### 7.1. Adverse Events

Summary tables will be provided for all treatment-emergent adverse events (TEAEs). Treatment-emergent AEs are defined as events whose onsets occur, or severity worsens on or after the date of first dose of study drug. All TEAEs will be included in summaries.

An overview table will contain the number and percentage of patients with any TEAEs, with study drug related TEAEs, serious adverse events (SAEs), with AEs causing death, with related AEs causing death, with related SAEs, with AEs causing study drug discontinuation, and with AEs causing discontinuation from the study.

The TEAE summary tables will include counts of patients. Therefore, if a patient experiences more than one episode of a particular TEAE, the patient will be counted only once for that event. If a patient has more than one AE that is coded to the same preferred term, the patient will be counted only once for that preferred term. Similarly, if a patient has more than one TEAE within a SOC, the patient will be counted only once in that SOC.

All AEs are to be reported from the time of first administration of study drug until study completion or discontinuation. The severity of all AEs is recorded as mild, moderate, or severe. If severity is missing for TEAE, it will be set to severe. If severity is missing for AE at pre-treatment, the severity will be set to mild: if severity change is not reported during the study, then severity of mild is retained for analysis. A treatment-related AE is defined as an AE with relationship to study drug recorded as related or missing in the CRF. All AEs will be coded using the MedDRA (Version 10.1).

The maximum severity of AE is defined as the AE with the worst severity experienced overall during the study, within a SOC, or within a preferred term.

The following TEAE summaries will be presented:

- Frequency of TEAEs by preferred term, sorted by decreasing overall total
- Frequency of TEAEs related to study drug, by SOC and preferred term
- Frequency of TEAEs related to study drug by preferred term, sorted by decreasing overall total
- Frequency of TEAEs by maximum severity, SOC, and preferred term
- Frequency of AEs causing discontinuation from the study drug and study by SOC and preferred term
- Frequency of SAEs by SOC and preferred term
- Frequency of TEAEs with seriousness of fatal by SOC and preferred term.

Listings will be presented to show SAEs, AEs that resulted in early discontinuation from the study or study drug, and AEs with seriousness of fatal. A listing of all reported AEs will also be presented. For each adverse event the following will be specified: the treatment group, MedDRA system organ class, preferred term and adverse event description from the CRF, onset and resolution dates and their respective study days, duration, time of onset, severity, seriousness, AE or current condition number associated with the AE, and relationships to study procedure, the study drug and concomitant medication. The listing will display the outcomes as reported by the investigator.

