#### **5.3.2 Baseline**

After enrollment but prior to application of HyBryte the following assessments will be performed:

Interval medical history from screening obtained

Complete Physical Examination

Vitals taken (heart rate, respiratory rate, and sitting blood pressure)

Hematology panel drawn

Clinical chemistry panel drawn

Pregnancy test results reviewed

Three lesions that are representative of the patient's disease and are discrete with defined borders, will be chosen as the index lesions, and classified as patch or plaque lesions

Charting of all CTCL lesions on the "Body Lesion Diagram" form ([Appendix II](#)) locating and numbering each of the index lesion

Each of the index lesions will have a CAIIS score assessed and recorded

The mSWAT score will be assessed and recorded

5 mL of blood obtained and processed for serum hypericin levels

12-lead ECG obtained including QT interval measurements

The patient will complete the Skindex-29 ([Appendix III](#)) and VASitch forms and the data transcribed into the eCRF

A jar of ointment will be issued and the weight of the jar prior to dispensation will be recorded

Only after all of the above have been completed, patients will be instructed on proper drug application and demonstrate proficiency in drug application and all accessible lesions will be treated with study drug

The weight of the jar after drug application will be recorded

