### 8.1 Definitions

#### 8.1.1 **Adverse Event (AE)**

Any noxious or unintended event that occurs in association with the use of an investigational agent in humans, ***whether considered related to the investigational agent or not.*** This definition encompasses symptoms or signs reported by the subject or detected by the investigator or other competent observer, as well as medically important deviations from normality in the results of ancillary investigations. If present at time of first dose of study drug, such AEs must be recorded as part of the medical history.

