#### 8.1.2 **Treatment-Emergent AE**

An AE that is new in onset or aggravated in severity or frequency following entry into the study. In addition, any pathological finding on physical examination or diagnostic procedure that is new in occurrence or exacerbated in comparison with the subject's status at study entry is considered a treatment-emergent AE if it requires any medical or surgical intervention whatsoever (including, but not limited to, additional diagnostic procedures or alteration of prescribed therapy).

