## INTRODUCTION

This statistical analysis plan (SAP) provides a more technical and detailed elaboration of the statistical analyses of safety, pharmacokinetics (PK), and lesion response as outlined and/or specified in Amendment 1 of the final study protocol dated 22 April 2022.

Any deviations from this SAP will be described and justified in the Clinical Study Report (CSR). The preparation of this SAP has been based on International Conference on Harmonisation (ICH) E3 and E9 guidelines [1, 2]. If the protocol is subsequently amended, this SAP will be amended as well, if warranted. Should the SAP and the protocol be inconsistent with respect to the planned analyses, the language of the SAP prevails.

All data analyses and generation of TFLs will be performed using SAS® version 9.4 or higher. The SAP will be finalized and signed off prior to locking the database and subsequent unblinding of treatment arm assignments.

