## 8. APPENDIX 1: DATA HANDLING CONVENTIONS

### 8.1. Missing Severity Assessment for Adverse Events

If severity is missing for an AE started prior to the first study medication, then a severity of “Mild” will be assigned. If the severity is missing for an AE started on or after the first study medication dosing, then a severity of “Severe” will be assigned. The imputed values for severity assessment will be used for incidence summary, while the actual missing values will be presented in data listings.

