### 8.3. Missing Date Information for Adverse Events

The following imputation rules only apply to the case where the date is incomplete (i.e., partial missing) for adverse events. *Missing day and month*

- If the year is same as the year of first day on study medication, then the day and month of the start date of study medication will be assigned to the missing fields.
- If the year is prior to the year of first day on study medication, then December 31 will be assigned to the missing fields.
- If the year is after the year of first day on study medication, then January 1 will be assigned to the missing fields.

*Missing month only*

- Treat day as also missing and replace both month and day according to the above procedure.

*Missing day only*

- If the month and year are same as the year and month of first day on study medication, then the start date of study medication will be assigned to the missing day.
- If the month and year are before the year and month of first day on study medication, then the last day of the month will be assigned to the missing day.
- If the month and year are after the year and month of first day on study medication, then the first day of the month will be assigned to the missing day.

If the stop date is complete and the imputed start date as above is after the stop date, the start date will be imputed by the stop date.

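### SAP 7.1 leaves worsening frequency out of the treatment-emergent definition, so a pre-existing symptom that becomes more frequent is counted or missed according to how the site records it

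*SAP*

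**What the plan says.** Five statements bear on the point.

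- **SAP 7.1, definition:** "Treatment-emergent AEs are defined as events whose onsets occur, or severity worsens on or after the date of first dose of study drug". There are two ways in: a new onset, or worse severity.
- **Protocol 8.1.2, first sentence:** "An AE that is new in onset or aggravated in severity or frequency following entry into the study". This adds a third way in, frequency, and it starts the clock at study entry. (Its second sentence, on findings that need intervention, is not at issue here.)
- **Protocol 8.1.1, on what is already there:** "If present at time of first dose of study drug, such AEs must be recorded as part of the medical history".
- **SAP 7.1, reporting window:** "All AEs are to be reported from the time of first administration of study drug until study completion or discontinuation".
- **SAP Introduction, precedence:** "Should the SAP and the protocol be inconsistent with respect to the planned analyses, the language of the SAP prevails".

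The SAP gives no reason for leaving frequency out.

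**The concern.** Safety is the secondary objective in the protocol and is listed among the secondary objectives in the SAP. The TEAE tables are a main output for it, and by the precedence clause they follow the SAP's narrower rule.

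Patients enter with active lesions on at least 10% of body surface. Some may already have itch, burning or pain at those lesions; the documents give no prevalence, so this is an assumption. A twice-weekly skin treatment could make such a symptom more frequent without making any one episode worse.

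Protocol 8.1.1 sends the pre-existing symptom to medical history. Unless the site opens a new record, worsening is then its only way into the tables, and the SAP recognises worsening in severity alone. The risk is that the same patient experience is counted at one site and not at another because of data-entry habit.

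**Working it through.** The documents state no figure that rests on this definition, so there is nothing to reproduce. The check is a literal comparison of the rules, followed by the weight of one patient.

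**Step 1. Classify six kinds of event.** The last column applies the SAP definition together with the SAP's own reporting window.

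| Event | Protocol 8.1.2 | SAP 7.1 definition | SAP 7.1 definition and window |
|---|---|---|---|
| 1. Pre-existing, more frequent after dosing, same severity, one ongoing record | yes | **no** | **no** |
| 2. As 1, but each episode entered with its own post-dose onset | yes | yes | yes |
| 3. Pre-existing, more severe after dosing | yes | yes | yes |
| 4. New on the Baseline date, before application | yes | yes | no |
| 5. New after study entry, before the Baseline date | yes | no | no |
| 6. New after first application | yes | yes | yes |

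Rows 1 and 2 describe the same clinical course and differ only in how it was entered. That is the defect. Rows 4 and 5 concern the start point. Row 4 is yes under protocol 8.1.2 because protocol 5.3.2 places Baseline after study entry: "After enrollment but prior to application of HyBryte the following assessments will be performed".

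**Step 2. Ask whether the data could support a frequency rule.** Protocol 8.4 lists what is noted for each AE: start and resolution dates, severity, relationship, action taken and outcome. Frequency is not among them. Adding the word to the SAP would not by itself let a programmer find row 1 events; the site must also give the aggravation its own onset date.

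**Step 3. Weight of one patient.** Inputs: about 6 patients planned (protocol 5.1), at most 8 with replacements (protocol 5.4), and all enrolled patients in the denominator (SAP 5.2). The shift is 100 × k / N percentage points for k reclassified patients. The documents do not give k; the values 0 to 2 are assumed to show a range.

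| k (assumed) | N = 6 | N = 8 |
|---|---|---|
| 0 | 0.0 | 0.0 |
| 1 | 16.7 | 12.5 |
| 2 | 33.3 | 25.0 |

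These shifts follow from the size of the trial and would apply to any reclassified event. They do not estimate the effect of this definition.

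**The case against.** **The SAP matches Phase 3.** The note under protocol Table 2 defines a Phase 3 TEAE as new or worse in severity after first dose, with no frequency criterion. The sponsor may want that consistency. This stands as a possible reason, but the SAP does not give it, and this trial's protocol says otherwise. It also means that the Table 2 rates (pruritus 12/161 = 7.5%, application site pain 16/161 = 9.9%) are not a like-for-like yardstick for a count that includes frequency.

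**Little would go unseen.** Episodes with their own post-dose onset still count. SAP 7.1 lists every reported AE with onset date and time of onset. Skindex-29 asks how often skin hurts, burns and itches, and its change is summarised (SAP 6.3). Itch is scored at every light session, and erythema is graded before and after each one. Most of this stands, and it limits the harm. It does not correct the summary counts, and the AE listing holds only what was entered as an AE. A symptom left as a medical-history line would not be in it.

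**A stronger reading is tempting.** A reader might infer that the SAP's calendar-date start departs from a first-dose start in the protocol, and that events arising at Baseline before the ointment will be counted as TEAEs. The documents do not support this. Protocol 8.1.2 starts at study entry, so on its literal wording such an event is already treatment-emergent (row 4). The SAP's reporting window opens only at first administration, protocol 8.1.1 sends events present at first dose to medical history, and neither schedule (protocol Table 3, SAP Table 10) has AE collection at Baseline.

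What remains is a mismatch within SAP 7.1 between the date and the time of first dose. It could matter only in two cases. One is a pre-dose event entered as an AE, which SAP 8.1 foresees ("If severity is missing for an AE started prior to the first study medication"). The other is a partial onset date in the month of first dose, where under SAP 8.3 "then the start date of study medication will be assigned to the missing day".

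**Conclusion.** The point holds for frequency. The SAP's definition is narrower than the protocol's, the SAP governs the tables, and a pre-existing symptom that becomes more frequent at unchanged severity is omitted when it is kept as one ongoing record and counted when its episodes are entered separately.

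The number of patients affected cannot be derived and may be zero. It depends on how many patients have intermittent symptoms at entry and on how sites date an aggravation, and the documents give neither. In an exploratory, descriptive study of 6 to 8 patients the consequence is limited to the reliability of the TEAE counts; no primary endpoint is touched.

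The start point is a lesser matter. The documents use study entry, date of first dose and time of first administration, and one should be chosen. They do not show that pre-dose Baseline-day events will be counted, and the point does not rest on that.

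**What to change.** Before database lock:

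1. **Reword SAP 7.1.** Define TEAEs as *events whose onset occurs, or whose severity or frequency worsens, after first application of study drug*.
2. **Instruct the sites.** A pre-existing symptom that becomes more frequent is entered as an AE with its onset at the date of aggravation. The existing start-date field then carries the information and no frequency field is needed. Where visits are already complete, this means a query against the medical-history entries.
3. **Declare the start point.** Say that first application is chosen in place of the study entry used in protocol 8.1.2, in line with protocol 8.1.1 and the SAP's own reporting window. Rows 4 and 5 above then fall outside the TEAE count by stated choice.
4. **Carry the change into SAP 8.3.** State that an event whose partial date is imputed to the first-dose date still counts as treatment-emergent, so that the new wording does not undo the present rule.

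The cost is a few sentences, a short site instruction and possibly some queries. Slightly more TEAEs may be reported, and the counts become slightly less comparable with the severity-only Phase 3 table; a footnote to the TEAE tables can say so.

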### 8.2 Relationship to Study Drug

The relationship of an AE to the assigned study drug is assessed using the following definitions:

- **Not Related:** The drug experience is clearly related to other factors such as the patient's/subject's clinical state, therapeutic interventions or concomitant drugs.
- **Possibly Related:** The drug experience follows a reasonable sequence from the time of drug administration and/or follows a known response pattern to the

study drug, but could have been produced by other factors such as the patient's/subject's clinical state, therapeutic interventions or concomitant drugs.

- **Related:** The drug experience follows a reasonable temporal sequence from the time of drug administration and follows a known response pattern to the study drug, and cannot be reasonably explained by other factors such as the patient's/subject's clinical state, therapeutic interventions or concomitant drugs.

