### 8.4 Recording Adverse Events

All AEs, whether judged to be related or not to the study drug, should be recorded in both the medical record and the CRF. The start and resolution dates, the judgment of the severity of the AE, the judgment of the relationship of the AE to the study drug, the action taken for subsequent dose of study drug, and the outcome should be noted.

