### 10.2 Analysis of Safety

Listings of findings per patient will be provided. Average and median results for laboratory findings, vital signs, ECG findings and PK outcomes will be provided. Any significant outliers ( $>2x$  the standard deviation) will be highlighted. Listings of AEs within 48 hours of ointment application will be tabulated. Any serious or related AEs determined within 14 days of last drug application will be tabulated, in addition to any medications received during the 10-week period.

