### 8.2. Missing Relationship to Study Drug for Adverse Events

If the relationship to the study medication is missing for an AE started after baseline, a causality of “Related” will be assigned. The imputed values for relationship to study medication will be used for incidence summary, while the actual values will be presented in data listings.

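### SAP 7.1 counts related and unassessed AEs as treatment-related but never places the protocol's Possibly Related grade, so five planned outputs, read literally, leave those events out

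*SAP*

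**What the plan says.** Protocol section 8.2 defines three causality grades: Not Related, Possibly Related and Related. The middle grade is for an event that fits the timing of dosing or a known response pattern, "but could have been produced by other factors such as the patient's/subject's clinical state", other treatments or concomitant drugs. Protocol section 8.4 requires "the judgment of the relationship of the AE to the study drug" to be noted for every AE in the medical record and the CRF.

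SAP section 7.1 turns this into an analysis category: "A treatment-related AE is defined as an AE with relationship to study drug recorded as related or missing in the CRF". SAP section 8.2 adds a rule that begins "If the relationship to the study medication is missing for an AE started after baseline" and assigns the value Related for the incidence summaries.

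The category is then used in the overview table, which has a row for patients with study-drug-related TEAEs and further entries "with related AEs causing death, with related SAEs". It is used again in two summaries: "Frequency of TEAEs related to study drug, by SOC and preferred term", and the same by preferred term alone, sorted by frequency. Protocol section 10.2 has a tabulation of its own that uses the word without defining it: "Any serious or related AEs determined within 14 days of last drug application will be tabulated".

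**The concern.** The protocol's scale has three grades, and the SAP's definition accounts for one of them plus missing values. Not Related is excluded by its name. Possibly Related is not mentioned anywhere in the SAP.

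Read literally, the definition gives an ordering that is hard to defend. An event nobody assessed counts as drug-related. An event that the investigator assessed and could not separate from the drug does not. Treating missing causality as Related is a cautious choice, and dropping the middle grade works against it.

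Safety is a secondary objective in both documents, and the related-AE summaries are part of how it will be reported. If the grouping is left open, two programmers could produce different tables from the same data. In an open-label trial the choice could also be made with the events already in view.

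**Working it through.** The plan gives no figure to reproduce here. The check sets the texts side by side, counts the outputs, and works out what one patient is worth.

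**Classification under SAP 7.1 as written**

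| Value under protocol 8.2 | Counted as treatment-related? | Basis |
|---|---|---|
| Related | Yes | SAP 7.1 |
| Missing | Yes | SAP 7.1; set to Related by SAP 8.2 |
| Possibly Related | No | Not named in any SAP section |
| Not Related | No | Not named; negative grade |

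Two details support the literal reading. SAP 7.1 keys on the value recorded in the CRF, which points to a field entry rather than a general idea. SAP 8.2 uses Related as the value to assign, and that is the name of one protocol grade. The protocol's scale does not repair the definition, because the SAP Introduction says the SAP prevails where the two documents differ on planned analyses.

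**Outputs that depend on the definition (SAP 7.1)**

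- Overview table: related TEAEs, related AEs causing death, related SAEs = 3 rows.
- Frequency tables: related TEAEs by SOC and preferred term, and related TEAEs by preferred term = 2 tables.
- Total: 3 + 2 = 5 outputs, held in three physical tables.

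**Weight of one patient in the related-TEAE incidence**

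Inputs: about 6 patients (protocol 5.1), and a ceiling of 8 with replacement (protocol 5.4). Take *k* patients who have at least one Possibly Related TEAE and none graded Related or missing. The incidence falls by 100 × *k*/*n* points.

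| *k* | *n* = 6 | *n* = 8 |
|---|---|---|
| 0 | 0 | 0 |
| 1 | 1/6 = 16.7 | 1/8 = 12.5 |
| 2 | 2/6 = 33.3 | 2/8 = 25.0 |

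The value of *k* cannot be obtained from the documents. Even when *k* is 0 the preferred-term tables can lose counts. A patient with one Related event and one Possibly Related event under a different term stays in the overview row but drops out of the second term's row.

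**Is the middle grade likely to be used?** This is inference. Protocol 8.2 reserves Related for events that other factors, including the patient's clinical state, cannot reasonably explain. Pruritus and erythema were both reported with the drug in Phase 3 (12 and 7 of 161 patients, protocol Table 2). Both can also come from the disease itself, so Possibly Related would be a natural grade for them.

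**The case against.** The strongest reply is that the omission turns on a form that is not among the documents. SAP 7.1 refers to what the CRF records, and protocol 8.4 does not list the response options. If the field is a yes/no item, or if related was meant to cover everything except Not Related, no event is lost. An umbrella meaning would also suit the SAP's habit of resolving doubt cautiously: missing causality becomes Related and missing on-treatment severity becomes Severe. This stands as a limit on what can be claimed. It is certain that the SAP is silent on the grade; it is not certain that events will be dropped. It does not remove the need for a statement, because the intended meaning is not written down.

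The second reply concerns importance. No test or decision rule uses the related-AE rate, and the named secondary endpoints are laboratory tests and vital signs. SAP 7.1 also says "A listing of all reported AEs will also be presented", with relationship to study drug shown for each event. With about six patients, a reader could recount by hand. All of that is correct and keeps the point modest. The summary tables should still not need correcting from the listing.

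Third, 16.7 and 12.5 points are simply the weight of one patient in any percentage here. That is true. They show the step size and are not an estimate of harm.

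Finally, SAP 7.1 and 8.2 differ on missing causality for events that began before treatment: 8.2 imputes only for events starting after baseline, while 7.1 has no such limit. That is a separate matter and does not affect this one.

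**Conclusion.** The concern holds. As written, the SAP's definition leaves out a causality grade that the protocol tells investigators to use, while counting events with no grade at all. Five outputs are affected, and under the literal reading the error can only reduce the number of events reported as drug-related.

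The size is unknown and may be nil; the arithmetic gives only the step per affected patient. The conclusion assumes that the CRF carries the protocol's three grades and that related in SAP 7.1 means the grade of that name. If the word was meant more broadly, the fault is an undefined term and the same sentence cures it.

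The all-TEAE, maximum-severity, SAE, discontinuation and fatal-event tables are unaffected, as are the ECG and hypericin analyses. The definition should be corrected, but it does not threaten the study's main results.

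**What to change.** Replace the definition in SAP 7.1 with: *A treatment-related AE is an AE with relationship to study drug recorded as Related or Possibly Related, or missing.* Apply it to the three overview rows and the two related-TEAE frequency tables. State in the SAP that related has the same meaning in the protocol 10.2 tabulation of serious or related events within 14 days of the last application.

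Check the CRF causality field. If it does not carry the protocol's three grades, say in the SAP how its options map to them. The AE listing needs no change, since it already shows relationship to study drug.

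The cost is one sentence and one field check before database lock, with no new data. The reported related-AE rate may come out slightly less favourable.
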